5.6.9.2 Presentations

The number and percentage of participants with AE LLTs involving clinical TLS and laboratory TLS by maximum CTCAE grade will be presented, including the total number of AEs. Figures for laboratory TLS and clinical TLS will be presented. Bar charts showing the number of TLS AEs and the number and percentage of participants having TLS AEs by week since AZD4573 administration will be presented. TLS-associated AEs will be listed with other AEs.

Time from infusion to onset of TLS after first AZD4573 administration and after subsequent doses will be summarised using TLS monitoring data. Listing of TLS monitoring will be presented including uric acid, potassium, phosphate, calcium, urea nitrogen, creatinine, creatinine elevation due to TLS, cardiac arrhythmia due to TLS, seizure due to TLS and Cairo-Bishop grades for clinical TLS.

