8.3.2 Follow-up of AEs and SAEs

Any AEs that are unresolved at the participant's last assessment in the study are followed up by the investigator for as long as medically indicated, but without further recording in the eCRF. AstraZeneca retains the right to request additional information for any participant with ongoing AE(s)/SAE(s) at the end of the study, if judged necessary.

After the initial AE/SAE report, the Investigator is required to proactively follow each participant at subsequent visits/contacts. All SAEs and non-serious AEs will be followed until resolution, stabilisation, the event is otherwise explained, or the participant is lost to follow-up.

Adverse event variables

The following variables will be collected for each AE:

- AE (verbatim)
 - The capture of diagnoses is preferred over all associated signs and symptoms. For example: laboratory TLS, clinical TLS, cytokine release syndrome. Provisional diagnoses (eg, PHL) must be updated as soon as possible.
- The date when the AE started and stopped
 - When the onset of an AE in relation to dosing is rapid, for example TLS, it is important to record the **exact time of the start of infusion** dosing and the **time of AE onset** in addition to the dates.
- CTCAE grade/changes in CTCAE grade
- **For TLS events:** Adverse events of TLS shall be graded according to CTCAE. The AE verbatim shall discriminate between laboratory and clinical TLS. In addition, TLS events will be graded according to Howard modification of the Cairo-Bishop grading system (see [Appendix G](#)) on the TLS monitoring eCRF form.
- Whether the AE is serious or not

- Investigator causality rating against the IP(s) (yes or no)
- Action taken with IP(s) in response to the AE (for example: no action, dose reduced, treatment temporarily stopped, treatment permanently discontinued).
- Outcome of the event

In addition, the following variables will be collected for SAEs:

- Date AE met criteria for SAE
 - The date of start of first signs and symptoms should be captured together with the date the event became serious.
- Date investigator became aware of SAE
- Reason AE is classified as serious
- Date of hospitalisation
- Date of discharge
- Probable cause of death
- Date of death
- Autopsy performed (yes/no)
- Causality assessment in relation to Study procedure(s)
- Causality assessment to other medication

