10.6.2.1.2 TLS Monitoring and Management

Please refer to [Appendix G](#) for the definition of TLS and the TLS grading criteria to be used in this study.

All participants will receive TLS prophylaxis during the intra-participant dose ramp-up and be monitored for TLS during the first 24 hours post start of infusion during the intra-participant dose ramp-up (see Sections [10.6.2.1.1](#) and [10.6.2.1.2](#)). If there are no signs of TLS at the 6 hour TLS monitoring assessment, the participant can be managed as an outpatient at the discretion of the investigator and return to the clinic the next day to complete the 24 hour TLS monitoring assessment. Participants showing signs of TLS at 6 hours after the start of infusion must remain admitted for inpatient TLS monitoring approximately every 6 hours (or more frequently if clinically indicated) until the 24 hour TLS monitoring assessment.

Where hospitalisation for longer than the mandated 24 hours is required it should be noted that if this is due to occurrence of an AE then the event must be reported as an SAE, per definition. However, if it is purely for the purposes of extended observation then this does not qualify as an SAE and does not need to be reported.

For all participants, results of safety laboratory testing (haematology and clinical chemistry at a minimum) must be available within 72 hours prior to dosing and must be reviewed by the investigator prior to each administration of AZD4573. For each TLS monitoring timepoint, a TLS Monitoring page in the eCRF is to be filled out.

In particular, the uric acid level must be < ULN prior to the start of each AZD4573 infusion.

It is strongly recommended that for all participants with elevated uric acid (hyperuricaemia) and intermediate/high risk of TLS, prophylaxis should be administered prior to AZD4573 per Section 10.6.2.1.1 and repeated as clinically indicated thereafter as per local standard.

Monitoring for TLS includes checking potassium, calcium, phosphate, uric acid, and creatinine. Fluid balance must be monitored according to institutional standards.

Any participant developing laboratory TLS must be treated promptly for electrolyte abnormalities (such as hyperkalaemia) to prevent arrhythmias/seizures and for elevated uric acid (hyperuricaemia) with rasburicase (0.20 mg/kg/d IV over 30 minutes for up to 5 days) to prevent acute renal failure and monitored closely for signs of progression to clinical TLS.

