- **Pregnancy:** a urine or serum sample for a pregnancy test will be collected from all female participants of childbearing potential at the following timepoints:
 - Screening
 - Pre-dose on Cycle 1, Day 1
 - Prior to initiating a new cycle (once every 21 days)
 - At the 30-day follow-up visit.Urine β -hCG and quantitative serum β -hCG tests are permitted. If a urine β -hCG test is positive or indeterminate, quantitative serum β -hCG will be performed for confirmation. Additional testing may be performed at investigator discretion for example in the event of suspected contraception failure.
- **Cardiac:** Cardiac troponin measurements are required at:
 - Screening.
 - Cycle 1: pre-dose (up to 2 hours prior to infusion) and at 24 hours after start of infusion.
 - Cycle 2+: pre-dose (up to 2 hours prior to infusion).
 - 30-Day follow-up visit.
- **TLS monitoring:** potassium, calcium, phosphate, uric acid, and creatinine at baseline, then at the following timepoints for each infusion: prior to infusion, 6 hours after start of infusion, and 24 hours after start of infusion during the intra-participant ramp-up. Participants showing signs of laboratory TLS at 6 hours after infusion must be admitted for inpatient TLS monitoring for 24 hours and monitored every 4 to 6 hours during this time (or more frequently if clinically indicated); see Section [10.6.2.1.2](#).
- **Liver chemistry tests:** GLDH and CPK, will be measured at screening for all participants.

For any participant on study who experiences elevated ALT/AST ($\geq 3 \times$ ULN) and/or elevated total bilirubin ($\geq 2 \times$ ULN), repeated liver chemistry tests are required including: total and direct/indirect bilirubin, ALT, AST, ALP, C-reactive protein, CPK, GLDH, INR/PT, fibrinogen, D-dimer (where available at local institution). Liver chemistry tests should be measured at least every 48 hours (-2/+12 hours) post start of infusion until resolution of the event to baseline (or Grade 1) levels.

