5.6.9 Tumour lysis syndrome

5.6.9.1 Definitions and Derivations

Tumour lysis syndrome (TLS) is an important identified risk for AZD4573. TLS prophylaxis is mandatory for all participants starting 3 days before the first dose of AZD4573, which should be followed in addition to institutional guidelines.

There are 2 data sources to report TLS: AEs of TLS and TLS monitoring data. One TLS AE per infusion per participant will be counted. For participants with multiple TLS AEs recorded after one infusion, only the TLS AE with maximum CTCAE grade will be counted for reporting purposes. Similar rules apply to TLS monitoring data. According to the TLS monitoring schedule in the CSP, participants could have multiple TLS monitoring episodes after one infusion, if counting TLS monitoring assessments at each unique date and time per participant as an episode. For reporting purposes, a maximum of one TLS per infusion per participant will be counted. The highest Cairo-Bishop grade of each clinical characteristic (creatinine abnormality, cardiac arrhythmia, seizure) and overall grading will be computed for each infusion and participant.

Overall Cairo-Bishop grading for Clinical TLS is defined as the maximum overall on treatment Cairo-Bishop grading, derived from the highest contributing grade (creatinine abnormality, cardiac arrhythmia, seizure) for a specific episode of clinical TLS.

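### Time to TLS onset is summarised from monitoring checks scheduled at about 6 and 24 hours, so it reports first detection; the AE onset times the protocol asks for are not used at hour level

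*SAP*

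**What the plan says.** SAP 5.6.9.1 recognises two sources: "There are 2 data sources to report TLS: AEs of TLS and TLS monitoring data". For time to onset, SAP 5.6.9.2 names only the second: "Time from infusion to onset of TLS after first AZD4573 administration and after subsequent doses will be summarised using TLS monitoring data".

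Protocol 10.8.2.5 schedules the TLS laboratory checks "prior to infusion, 6 hours after start of infusion, and 24 hours after start of infusion during the intra-participant ramp-up". If there are signs of laboratory TLS at 6 h, the participant is admitted and "monitored every 4 to 6 hours during this time (or more frequently if clinically indicated". Protocol 10.6.2.1.2 adds: "For each TLS monitoring timepoint, a TLS Monitoring page in the eCRF is to be filled out". SAP 5.6.9.1 distinguishes monitoring records by when the assessment took place: "if counting TLS monitoring assessments at each unique date and time per participant as an episode".

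For adverse events, protocol 8.3.2 says: "When the onset of an AE in relation to dosing is rapid, for example TLS, it is important to record the" infusion start time, continuing "dosing and the time of AE onset in addition to the dates". In SAP 5.6.9.2 the timing stated for TLS AEs is bar charts by week since administration. AE listings that derive days since last dose do so in whole days (SAP 4.1.3.1). The SAP also plans figures for laboratory and clinical TLS but does not describe their content.

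**The concern.** A monitoring record is dated by the check, not by the event. Between a clean check and the next positive one, onset is known only to lie in the interval. If the time of the positive check is summarised as a continuous time to onset, the median and range mainly describe the visit schedule.

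The SAP also gives no rule for which record defines onset. Section 5.6.9.1 keeps at most one TLS per infusion and computes the highest Cairo-Bishop grade. If the highest-grade record rather than the first positive one were used, onset would move later still.

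TLS is an important identified risk and an adverse event of special interest, so its timing after dosing is likely to be read closely. The protocol asks sites for a more direct time, and the plan does not state a use for it at hour level.

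**Working it through.** The plan gives no figure for time to TLS onset, so there is none to reproduce. The check is what the schedule does to a true onset time.

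**Inputs**
- Scheduled checks: pre-infusion, 6 h and 24 h after start of infusion (protocol 10.8.2.5).
- A participant clean at 6 h has no further scheduled check until 24 h (protocol 10.6.2.1.2 and 10.8.2.5). The closer inpatient checks start after TLS has been seen at 6 h, so they do not change the time of first detection.
- The laboratory TLS definition runs to 7 days after therapy starts (protocol Appendix G), well past the last scheduled check.

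**Step 1: bounds, with no distribution assumed.** Take the recorded time as the first scheduled check at or after onset t.
- For 0 < t ≤ 6 h, recorded ≈ 6 h and lag = 6 − t, so at most 6 h. Example: t = 2 h gives 6 − 2 = 4 h.
- For 6 < t ≤ 24 h, recorded ≈ 24 h and lag = 24 − t, so just under 18 h at most. Examples: t = 8 h gives 24 − 8 = 16 h; t = 18 h gives 24 − 18 = 6 h.
- For t > 24 h there is no scheduled record.

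**Step 2: average lag if onset were uniform within each interval (assumption).** Mean lag = 6/2 = 3 h in the first interval and 18/2 = 9 h in the second.

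**Step 3: range under an assumed exponential onset with median m.** The documents give no TLS onset distribution, so m was varied from 4 to 24 h (1,000,000 simulated onsets each). The share after 24 h is 2^(−24/m); for m = 8 h this is 2^(−3) = 12.5%.

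| Assumed true median m (h) | Onset after 24 h | True median, onsets ≤ 24 h (h) | Schedule-based median (h) | Mean lag (h) |
|---|---|---|---|---|
| 4 | 1.5% | 3.9 | 6 | 6.8 |
| 8 | 12.5% | 6.6 | 24 | 7.6 |
| 12 | 25% | 8.1 | 24 | 7.6 |
| 18 | 40% | 9.3 | 24 | 7.7 |
| 24 | 50% | 10.0 | 24 | 7.6 |

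These figures ignore unscheduled checks and check windows. They show how a schedule-based median behaves; they do not predict this trial's result.

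**Step 4: is the alternative source there?** Protocol 8.3.2 asks for both times. SAP 5.6.2.1 has a rule for AEs with a missing start time, which implies that start time is a field. Protocol 8.3.6 makes TLS reportable irrespective of seriousness, and protocol 8.3.2 has the AE verbatim separate laboratory from clinical TLS. An AE-based summary split by type therefore looks feasible.

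**Step 5: do the protocol sections agree on the schedule?** The Schedule of Activities marks TLS monitoring across Cycle 1 Weeks 1 to 5, while 10.6.2.1.2 and 10.8.2.5 tie it to the dose ramp-up. The inpatient interval is approximately 6-hourly in 10.6.2.1.2 and 4- to 6-hourly in 10.8.2.5. These passages must be reconciled, because they determine which infusions and times can have scheduled monitoring records.

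**The case against.** The best defence is that AE times may be no sharper. Laboratory TLS is defined by serum values and clinical TLS presupposes laboratory TLS (protocol Appendix G), so onset is often known only when blood is drawn. This stands for laboratory TLS and for creatinine-based clinical TLS. It is weaker for arrhythmia or seizure, for events between checks or after 24 h, and for later infusions.

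A second defence is completeness: protocol 8.3.5 limits which laboratory changes become AEs. Special-interest reporting of TLS under 8.3.6 largely answers this, although some AE times may still be missing. It is also true that the eCRF is not among the documents, so a separate onset field on the monitoring page cannot be ruled out. The SAP describes only assessment date and time.

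Four stronger readings are tempting but not supported:
- *No monitoring data exist outside the ramp-up.* Protocol 8.3.2 puts Howard grading of TLS events on the monitoring form without limiting the period, and the Schedule of Activities covers Cycle 1 Weeks 1 to 5. What is missing is scheduled records.
- *The variable can read only 6 or 24 h.* Records carry the actual assessment time, and clinically driven checks can fall elsewhere. Values would cluster near those times.
- *The summary cannot show whether TLS appears before the outpatient decision.* That decision follows the 6 h check, and monitoring data do show whether TLS had been seen by then.
- *AE data would remove average errors of 3 h and 9 h.* Those averages assume uniform onset and AE times that equal true onset, and the documents establish neither.

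**Conclusion.** The point holds as one about labelling and choice of source. As described, the planned summary measures time to first detection on a coarse schedule and presents it as time to onset. Detection can trail onset by up to 6 h in the first interval and up to 18 h in the second; the average lag is unknown. After 24 h, or after infusions outside scheduled monitoring, inclusion depends on unscheduled entries. The conclusion assumes that the monitoring page carries assessment times only, and that sites record AE onset times as protocol 8.3.2 asks. The consequence is modest: one descriptive safety output, with no effect on ORR or any other efficacy result.

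**What to change.** In SAP 5.6.9.2:

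1. Add time to TLS onset as the earliest TLS AE onset date and time for each infusion minus the start-of-infusion time, for all infusions and separately for laboratory and clinical TLS. Specify the earliest AE explicitly, because SAP 5.6.9.1 otherwise keeps the AE with the maximum grade.
2. Keep the monitoring-based result, but call it first detection and tabulate it as 0 to 6 h, >6 to 24 h and >24 h, using the first positive record rather than the highest-grade one. Do not summarise it as a continuous onset time.
3. Where an AE onset time is missing, show the monitoring interval and report how many events this affects.

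Separately, reconcile the Schedule of Activities with protocol 10.6.2.1.2 and 10.8.2.5 on the monitoring period, and those two sections with each other on the inpatient check interval.

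For the SAP, the cost is a few sentences and one re-programmed descriptive output from data the protocol already asks sites to collect. The drawback is that some AE onset times may be missing.

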5.6.10 Electrocardiogram

5.6.10.1 Definitions and Derivations

Electrocardiogram (ECG) parameters will be assessed at baseline as well as throughout the study. ECG parameters include PR, RR, QRS, QT, QTcB, and QTcF. The QTcF is considered as the primary correction method to assess participant cardiac safety.

From these resting 12-lead ECGs values of the QT and RR intervals the QTcF and QTcB will be derived using the following formulae:

$QTcF = QT/RR^{(1/3)}$ where RR is in seconds

$QTcB = QT/RR^{(1/2)}$ where RR is in seconds

The values of QTcF (milliseconds) and QTcB (milliseconds) will be re-derived from the values of RR and QT during the creation of the reporting database.

The notable ECG interval values while on intervention are:

- Maximum QTcF and QTcB intervals > 470 milliseconds, > 480 milliseconds, and > 500 milliseconds.
- Maximum changes from baseline in QTcF and QTcB > 30, >60, and > 90 milliseconds.

5.6.10.2 Presentations

ECG parameters will be summarised using descriptive statistics by timepoint and change from baseline for each post-baseline timepoint. Absolute values and change from baseline for ECG data at each timepoint will be presented using boxplots.

The number and percentage of participants having notable ECG interval values on intervention will be summarised.

5.6.11 Echocardiogram

5.6.11.1 Presentations

Left ventricular ejection fraction results will be presented in listings.

5.6.12 Other Safety Assessments

5.6.12.1 Presentations

Serum immunoglobulins (IgA, IgM, IgG) will be listed and summarised descriptively. Absolute values and change from baseline values at each timepoint will be presented.

6 INTERIM ANALYSIS

There will be no interim analysis for Module 1.

8 APPENDICES

Appendix A Time windows for Module 1 – Efficacy assessments

Timepoint	Tumour assessments
After 8 weeks ^a	49 – 63
After 17 weeks	112 – 126
After 26 weeks	175 – 189

^a Participants who progress before the “After 8 weeks” timepoint should have had a tumour assessment performed at the time of progression. This tumour assessment will be used for the “After 8 weeks” timepoint.

SIGNATURE PAGE

This is a representation of an electronic record that was signed electronically and this page is the manifestation of the electronic signature

Document Name: d8231c00001-sap-ed-3		
Document Title:	Statistical Analysis Plan Edition 3	
Document ID:	Doc ID-004634337	
Version Label:	3.0 CURRENT LATEST APPROVED	
Server Date (dd-MMM-yyyy HH:mm 'UTC'Z)	Signed by	Meaning of Signature
18-Dec-2023 06:44 UTC	PPD [redacted] PPD	Author Approval
18-Dec-2023 11:44 UTC	PPD [redacted] PPD	Content Approval

Notes: (1) Document details as stored in ANGEL, an AstraZeneca document management system.
